8.3.2. Outcome definitions

8.3.2.1. Primary Endpoint (Primary Objective)

1. Proportion of patients eligible for sequence analysis that have any AA change from baseline in the epitope of sotrovimab binding in samples collected at Day 7, 14 and 28 (+/-2 days) (Primary Objective 1)
2. Proportion of patients eligible for sequence analysis that have any AA change from baseline in the spike protein in samples collected at Day 7, 14 and 28 (+/-2 days) (Primary Objective 2)

Laboratory process

Samples will be dispatched by sites (baseline sample) and patients or HCPs if patients are hospitalised (follow-up samples) to a central analytical laboratory which will follow its own procedures for sequencing techniques.

Sequence analysis of the SARS-CoV-2 spike gene will be attempted on swab samples from all participants eligible for sequence analysis. Viral load will also be measured for all samples. Changes in the spike protein that arise following treatment will be determined by comparing baseline and post-baseline sequencing data for a given patient. More detailed information will be available in the overarching study laboratory manual.

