4.2 Study Design

This is a phase IV, prospective cohort study amongst IC non-hospitalised patients treated with sotrovimab as part of standard clinical care to monitor the emergence of SARS-CoV-2 spike viral variants.

Patients will be followed for 28 days from the time they received sotrovimab treatment (index date (D0)) in one of the clinical sites. Data and samples will be collected following the schedule below (see also [Table 1](#))

Figure 1

- Non-hospitalised patients who are being treated with sotrovimab as part of standard of clinical care will be screened and enrolled if eligible (Day 0 = baseline). Informed consent, patient characteristics (demographic and clinical), and treatment history (related to COVID-19 and underlying diseases) will also be recorded at Day 0.
- Baseline nasal/oropharyngeal swab sample will be collected on site, as per protocol, under supervision after training and sent to the central analytical laboratory.
- Follow-up nasal/oropharyngeal swab samples (Day 7, 14 and 28 (+/- 2 days)) will be collected by the patients using home test kits or by healthcare professionals (HCP) in case of hospitalisation, as per protocol, with samples sent to the central analytical laboratory.

This document is confidential.

- Sequencing analyses will be conducted on all SARS-CoV-2 positive nasal/oropharyngeal swab samples that meet the threshold criteria for the sequencing assay.

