7.2 Safety Set

The Safety Set (SS) will include all participants who were enrolled and exposed to study intervention.

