8.2 Key Definitions

End of Study (EOS)

The EOS is defined as the date the last participant completes the last visit as shown in the Schedule of Activities in [Section 4.8](#).

Study day

Event date can be adverse events, labs, or any other assessments during the study.

If the event date \geq date of first dose of sotrovimab, study day = event date – date of first dose of sotrovimab + 1.

If the event date $<$ date of first dose of sotrovimab, study day = event date – date of first dose of sotrovimab.

Baseline Value

Baseline value will be defined as the last non-missing value recorded prior to sotrovimab administration or as close as possible to the end of sotrovimab infusion.

Retrospective collection of baseline data with the patient or directly with patient HCP will be conducted when not possible at Day 0. In all cases baseline is defined to be Day 0.

Change from Baseline (CFB)

CFB = Post-baseline value – Value at baseline

Treatment Emergent

Treatment emergent amino acid substitutions include subjects where baseline and post-baseline records exist.

Treatment emergence for consensus will include baseline records of allelic frequency $>5\%$ and post-baseline $>50\%$ as thresholds, whereas treatment emergence for minority will include baseline records of allelic frequency $>5\%$ and post-baseline $>5\%$ as thresholds.

Consensus sequence is defined as allelic frequency $>50\%$ and minority species with allelic frequency $>5\%$.

Lower Limit of Detection (LLOD)

LLOD of the assay is defined as 453 copies/mL (equivalent to Ct=38).

Lower Limit of Quantification (LLOQ)

LLOQ of the assay is defined as 1570 copies/mL (equivalent to Ct=36.18).

Viral load Negatives

The threshold to declare a viral load negative is the LLOD.

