10.1 Primary Efficacy Endpoint and Analysis

Primary efficacy analyses will be conducted for the safety populations.

The primary endpoints in this study are

- Proportion of patients eligible for sequence analysis that have any AA change from baseline in the epitope of sotrovimab binding.

The proportion of subjects with epitope amino acid change from baseline will be summarized showing the counts and percentages of patients in each epitope substitution change by post-baseline visits (Day 7, 14 and 28 (+/-2 days)) and overall and will be presented separately for Minority species (>5% allelic frequency) as well as consensus sequence (>50% allelic frequency).

Proportion of patients with epitope substitution change by VOC/VUI for Consensus Sequence (Allelic frequency >50%) and for Minority species (>5% allelic frequency) was also presented by visit for interim analysis reporting, but will not be included in the final analysis.

- Proportion of patients eligible for sequence analysis that have any AA change from baseline in the spike.

The proportion of subjects with spike amino acid change from baseline will be summarized showing the counts and percentages of patients in each spike substitution change by post-baseline visits (Day 7, 14 and 28 (+/-2 days)) and overall and will be presented separately for Minority species (>5% allelic frequency) as well as consensus sequence (>50% allelic frequency).

This document is confidential.

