10.2 Secondary Efficacy Endpoint and Analysis

Secondary efficacy analyses will be conducted for the safety populations, unless otherwise stated.

The secondary endpoints in this study are:

- Proportion of patients eligible for sequence analysis with SARS CoV-2 VOC/VUI on the earliest possible sample.

The proportion of patients with VOC/VUI will be summarized showing the counts and percentages of patients by each variants based on WHO classification and Pango sub-lineage for the earliest possible VOC/VUI sample including baseline. A data listing including WHO label and Pango sub-lineage will be provided.

- Proportion of patients with undetectable virus (i.e. viral load < LLOD)

Summary of proportion of patients with undetectable virus would be based on safety population and summarized by Day 7, 14 and 28 (+/-2 days).

- Clinical outcomes through Day 28 post-sotrovimab treatment:

The following clinical outcomes will be summarized by count and percentage of patients and its 95% CI by VOC/VUI, Non-VOC/VUI, and Overall:

- Proportion of patient with all-cause hospital admissions
- Proportion of patient with COVID-19 related hospital admissions.
- Proportion of patients requiring new or increased oxygen support (supplemental oxygen [not high flow], non-invasive ventilation or high-flow, invasive mechanical ventilation, or Extracorporeal membrane oxygenation [ECMO])
- Proportion of patient with all-cause ICU admissions.
- Proportion of patient with COVID-19 related ICU admissions.
- Proportion of patient who died through Day 28.
- Proportion of patient who died through Day 28 due to COVID-19.

In addition, the clinical outcomes would also be summarized by VOC/VUI variants and also by Medical Condition/Comorbidity.

The above outputs for Clinical outcomes will be based on the Safety Completers Population for the Interim Analysis and safety population for Final Analysis.

Data listings on clinical outcomes separately for hospital admission, ICU admission, oxygen support, death will be listed.

This document is confidential.

- AA (detected at >5% allelic frequency) changes in the SARS-CoV-2 spike protein in samples collected at Day 7, 14 and 28 (+/-2 days) compared to baseline following sotrovimab administration for samples with viral loads above the threshold of the sequencing assay

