- AA changes in the SARS-CoV-2 spike consensus sequences from baseline in samples where viral load is insufficient for >5% allelic frequency analysis but sufficient to generate consensus level sequencing data

For the above endpoints, Baseline and post-baseline (Day 7, 14 and 28 (+/-2 days)) AA substitutions will be summarized by showing the counts and percentages of patients in spike and epitope substitutions separately for Minority species (>5% allelic frequency) as well as consensus sequence (>50% allelic frequency).

Treatment emergent AA substitutions in spike as well as epitope for minority species and consensus sequence would be listed separately.

A similar baseline and post-baseline AA substitutions summary were presented by VOC/VUI variants for the interim but will not be included in the final analysis..

Data listings will be provided for all the baseline and post-baseline AA substitutions in spike as well as epitope for minority species and consensus sequence separately.

- Viral load

Absolute and change from baseline viral load summaries will be based on Safety and Virology population respectively on log10 copies/mL.

An overall summary of viral load (log10 copies/mL) with actual values and change from baseline values of viral load as well as by Day 0, Day 7, 14 and 28 (+/-2 days) using descriptive statistics will be displayed and presented graphically over time.

In addition, viral load (log10 copies/mL) with actual values and change from baseline values will also be summarized by VOC/VUI variants, and for Epitope Substitutions by Residue and presented graphically over time. Also, individual subject profile plots of viral load by VOC/VUI will be graphically presented based on viral load imputed values.

.A summary of viral load (log10 copies/mL) with actual values using descriptive statistics will be presented for the subset of subjects who had missing viral load at Baseline, and separately for the subset of subjects who had a viral load available at Baseline.

Listings will be provided for all viral load data as well as a separate listing including only epitope substitution.

This document is confidential.

- **Viral Rebound**

A subject has experienced a virologic rebound when following conditions are met:

If subject is in the safety population and:

- Viral load increases $>1 \log_{10}$ copies/mL at any point in time following any previous sample.
OR

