- The percentage of subjects will normally be calculated as a proportion of the number of subjects assessed for the analysis set presented. However, careful consideration is required in many instances due to the complicated nature of selecting the denominator, usually the appropriate number of subjects exposed. Details will be described in footnotes or programming notes, as necessary
- For categorical summaries (number and percentage of subjects) where a subject can be included in more than one category, a footnote or programming note will be added describing whether the subject is included in the summary statistics for all relevant categories or just 1 category as well as the selection criteria
- Where a category with a subheading (such as system organ class) has to be split over more than one page, output the subheading followed by '(cont)' at the top of each subsequent page. The overall summary statistics for the subheading should only be output on the first relevant page

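### The primary >5% amino-acid-change tables carry no viral-load condition, so samples good enough only for a consensus sequence can enter them and bias the proportion in either direction

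*SAP*

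**What the plan says.** **Population.** Both primary endpoints are proportions of patients eligible for sequence analysis. Protocol 8.3.2.1 says that sequencing "will be attempted on swab samples from all participants eligible for sequence analysis", but neither document defines that eligibility. SAP 7 lists four sets (Screened, Safety, Virology, Safety Completers), and none requires a sequence. SAP 10.1 assigns the analysis as follows: "Primary efficacy analyses will be conducted for the safety populations". SAP 7.2 defines that population: "The Safety Set (SS) will include all participants who were enrolled and exposed to study intervention". The table index labels the treatment-emergent tables (1.11-1.14, 1.47-1.48) Safety.

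**Scoring rule.** SAP 8.2 limits treatment-emergent substitutions to subjects with baseline and post-baseline records. It separates the consensus rule (baseline >5%, post-baseline >50%) from the minority rule, "whereas treatment emergence for minority will include baseline records of allelic frequency" >5% with post-baseline >5%. Neither rule mentions viral load, and minority has no upper frequency bound. SAP 10.1 reports both versions by visit and overall.

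**Two grades of sample.** In SAP 10.2, secondary objective 4 covers >5% changes "compared to baseline following sotrovimab administration for samples with viral loads above the threshold of the sequencing assay". Secondary objective 5 covers "AA changes in the SARS-CoV-2 spike consensus sequences from baseline in samples where viral load is insufficient for >5% allelic frequency analysis", provided the load still allows a consensus sequence. SAP 4.2 gives one laboratory gate for sequencing: "nasal/oropharyngeal swab samples that meet the threshold criteria for the sequencing assay".

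**The concern.** The plan recognises that some sequenced samples cannot show a change present at 5-50% frequency. It applies that distinction to two secondary endpoints but not to the primary >5% tables, where it matters most.

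Such a sample has a record, so it passes the paired-record rule.
- **Consensus-only at follow-up:** any 5-50% change is invisible, and the patient counts as unchanged. The proportion falls.
- **Consensus-only at baseline, adequate at follow-up:** a 5-50% variant that was already present is missed at baseline, seen later, and counted as emergent. The proportion rises.

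The study is descriptive, so no test is affected. But these proportions are the primary result and are reported to the regulator. A shift caused by sample quality would be read as more or less viral change under treatment.

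**Working it through.** **Step 1: the plan's own figures.** Protocol 8.5 uses the 95% score interval with continuity correction. Applied here it gives 45/500 = 9.0% (6.7-11.9) and 200/400 = 50.0% (45.0-55.0), both as stated. All eight rows of Table 2 reproduce, and 500/(1 - 0.20) = 625. The arithmetic of the study size is sound; the point concerns which samples count.

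**Step 2: can a consensus-only sample reach a >5% table under the written rules?**
- The gate in SAP 4.2 does not stop it. Objective 5 reports sequences from samples too low for >5% analysis, so those samples are sequenced.
- The paired-record rule in SAP 8.2 does not stop it, because a record exists.
- The allelic-frequency cut-offs do not stop it. With no upper bound on minority, a >50% call from such a sample also qualifies.
- The only numeric load limits in the SAP are the qPCR limits (LLOD 453 and LLOQ 1570 copies/mL). They are not thresholds for 5% calling, and no rule links them to amino-acid eligibility.

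**Step 3: illustrative size.** Inputs from Protocol 8.5: p = 20% (epitope) and 80% (spike) at 5% frequency; 9% and 52% at 15% frequency. These come from a trial in immunocompetent patients, and the protocol expects higher rates here. All shares below are assumptions.

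Observed proportion = p - c(p - q) + b(1 - p)r, where:
- c = share of pairs with a consensus-only follow-up sample;
- q = rate at which those pairs are scored positive, from 0 up to the 15%-frequency rate (changes above 50% are a subset of those above 15%);
- b = share with a consensus-only baseline and an adequate follow-up sample;
- r = share of patients without true emergence who carry a hidden 5-50% baseline variant.

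*Downward, one visit, 400 pairs, c = 25%, b = 0* (300 adequate pairs, 100 consensus-only):

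| | Adequate pairs only | All pairs, q = 0 | All pairs, q at upper limit |
|---|---|---|---|
| Epitope | 60/300 = 20.0% (15.7-25.1) | 60/400 = 15.0% (11.7-19.0) | 69/400 = 17.25% (13.8-21.4) |
| Spike | 240/300 = 80.0% (74.9-84.3) | 240/400 = 60.0% (55.0-64.8) | 292/400 = 73.0% (68.3-77.2) |

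At c = 10% the ranges are 18.0-18.9% (epitope) and 72.0-77.2% (spike).

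*Upward, b = 25%, c = 0:*
- Epitope: 0.20 + 0.25 × 0.80 × r = 22.0% at r = 10% and 26.0% at r = 30%.
- Spike: 0.80 + 0.25 × 0.20 × r = 80.5% and 81.5%.

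*Break-even, b/c = (p - q)/((1 - p)r), at r = 10%:*
- Epitope: 0.11/0.08 = 1.4 to 0.20/0.08 = 2.5.
- Spike: 0.28/0.02 = 14 to 0.80/0.02 = 40.

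For the epitope the balance depends on r. At r = 3%, 20% becomes 20.6% (b = 25%), and break-even is 0.11/0.024 = 4.6 to 0.20/0.024 = 8.3.

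**Step 4: limits of the model.** In the overall row, a patient with one consensus-only and one adequate follow-up sample can still be scored, so the downward figures are upper limits on dilution there. The upward term counts every hidden baseline variant as persisting above 5%, so those figures are upper limits for the given r and the break-even ratios are lower limits.

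**The case against.** **Unseen documents may already handle this.** Protocol 8.3.2.1 sends laboratory detail to the laboratory manual. SAP 5 has the sponsor's pipeline supply the substitution file under a data import agreement, and the shells are separate. Any of these could withhold 5% calls from low-load samples. The protocol abstract also ties >5% reporting to adequate load, although under secondary objective 4. This stands in part: a reader might infer that consensus-only samples will enter the primary tables, but the documents show only that they can. The protocol defers analysis detail to the SAP, however, and the SAP is silent.

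**The Safety label does not make every exposed patient the denominator.** A reader might infer that it does, so that an epitope rate of 20% with 80% of 500 patients evaluable would read 80/500 = 16.0%, or 50/500 = 10.0% with half evaluable. The documents do not support this as the likely reading. SAP 8.1 and 12.2.5.2 default to patients with data, SAP 8.2 requires paired records, SAP 12.2.4 separates the header N from the n analysed, and Protocol 8.5 treats low-load patients as not contributing. The contrary phrase in SAP 12.2.5.2, "complicated nature of selecting the denominator, usually the appropriate number of subjects exposed", is a generic table convention. What remains is an undefined eligibility term.

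**Objective 5 may be reported as intended.** The summaries for objectives 4 and 5 in SAP 10.2 are introduced as serving those endpoints and can be read as inheriting their sample restrictions. A claim that the low-load subset goes unreported is therefore not established.

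**There is mitigation.** Each primary endpoint is also tabulated at >50%, which consensus-only follow-up samples do not distort. Patient-level substitution and viral-load listings are planned, and Protocol 8.5 sends individual-level changes to the regulator. With the laboratory threshold in hand, affected pairs could be partly checked. This stands, but Table 1.43, as titled, does not separate consensus-only samples.

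**Conclusion.** The point holds for the >5% treatment-emergent tables. The written rule admits samples that cannot show the changes being counted, although the plan itself distinguishes them elsewhere.

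The true size is unknown, because the documents give no share of consensus-only samples at any visit. Under the assumed 25% follow-up share the single-visit loss is 2.75 to 5 points for the epitope and 7 to 20 points for spike. For spike at the planning rates, the net effect is downward unless low-load baselines far outnumber low-load follow-ups. For the epitope the direction turns on the assumed carriage of hidden baseline variants.

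The undefined eligibility term is a secondary point. Paired data are the likely denominator, but the SAP should say so. This should be fixed before the final analysis; it does not undermine the study.

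**What to change.** In SAP 7 and 10.1:

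- **(a) >5% treatment-emergent tables (1.13, 1.14, 1.48):** limit to patients with a baseline and at least one post-baseline sample, both above the laboratory's viral-load threshold for 5% calling, and state or cross-reference that threshold. The by-visit denominator is patients in this set with an adequate sample at that visit; the overall denominator is those with at least one.
- **(b) >50% treatment-emergent tables (1.11, 1.12, 1.47):** use patients with a baseline and at least one post-baseline consensus sequence. Flag consensus-only baselines, because SAP 8.2 compares with baseline at >5% and such a baseline cannot supply that.
- **(c)** State that these denominators override the subjects-exposed wording in SAP 12.2.5.2 for amino-acid tables.
- **(d)** Report how many Safety Set patients are not evaluable, by reason: no swab, undetectable virus, below threshold, no baseline sequence.

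If the laboratory manual or shells already filter such samples, (a) reduces to stating that rule in the SAP.

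**Cost:** SAP text, the population column of the index and shell headers; no new data collection. The evaluable N will be smaller and the intervals wider, and results may differ from the interim report, which the final report should note.

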8.7. Data analysis

8.7.1. Essential Analysis

This study is descriptive. Categorical variables will be described using counts, proportions and 95% CI and continuous variables will be described using measures of central tendency (e.g. mean, interquartile range, etc.)

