8.7.1.2. Secondary Objective

- VOC, VUI and other lineages information as classified by UKHSA and WHO will be identified from sequencing data for patients eligible for sequencing analysis (Secondary Objective 1)
 - This analysis will be done on the earliest possible sample and reported only once per patient as described in the SAP
- Comorbidities, clinical outcomes, patients with undetectable SARS-VoV-2 viral ribonucleic acid and safety events data will be described and reported with counts and proportions with a 95% CI (Secondary Objective 2 and 3).
- AA (detected at >5% allelic frequency) changes in the SARS-CoV-2 spike protein in samples collected at Day 7, 14 and 28 (+/-2 days) compared to baseline following sotrovimab administration for samples with viral loads above the threshold of the sequencing assay (Secondary Objective 4)
- AA changes in the SARS-CoV-2 spike consensus sequences from baseline in samples where viral load is insufficient for >5% allelic frequency analysis but sufficient to generate consensus level sequencing data (Secondary Objective 5)

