8.1 General Methods

- All participants entered into the database will be included in participant data listings.
- Quantitative (continuous) data including absolute values and changes from baseline, where appropriate, will be summarized with number of observations (n), mean, standard deviation (SD), median, interquartile range (IQR), minimum and maximum.
- For the summary statistics of all continuous variables unless otherwise specified, minimum and maximum will be presented to the same number of decimal places as the raw data. Mean, median, Q1, Q3, and IQR will be presented to one more decimal places than the raw data, and SD will be presented to two more decimal places than the raw data.
- Qualitative (categorical) data will be summarized using number of observations (n), and frequency and percentages of patients. Unless stated otherwise, the calculation of percentages will be based on the total number of patients with non-missing data. For some of the endpoints, 95% CI of proportion will also be displayed.
- All statistical analyses will be conducted using SAS® for Windows® Version 9.4 or higher.

This document is confidential.

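### Does the SAP drop the 95% confidence intervals that the protocol asks for on the primary endpoints and on undetectable virus?

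*SAP*

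**What the plan says.** The protocol sets a general rule for its essential analyses: "Categorical variables will be described using counts, proportions and 95% CI" (Protocol 8.7.1). Section 8.7.1.1, on the primary objective, sits under that rule and does not restate it. Section 8.7.1.2 is explicit for undetectable virus and clinical outcomes, which "will be described and reported with counts and proportions with a 95% CI".

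The SAP is less specific. In 10.1 the "proportion of subjects with epitope amino acid change from baseline will be summarized showing the counts and percentages of patients", and likewise the "proportion of subjects with spike amino acid change from baseline will be summarized showing the counts and percentages of patients". Both sentences go on to describe a display by individual substitution, for each post-baseline visit and overall. In 10.2 the text on viral clearance reads "Summary of proportion of patients with undetectable virus would be based on safety population and summarized by Day 7, 14 and 28", with no interval mentioned. The same section says of clinical outcomes: "The following clinical outcomes will be summarized by count and percentage of patients and its 95% CI". The general methods add: "For some of the endpoints, 95% CI of proportion will also be displayed" (SAP 8.1), without a list of endpoints or a method. SAP 17.1 refers the reader to a separate shells document for table content.

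Protocol 8.5 bases the study size on the precision of the two primary proportions. It uses the continuity-corrected score interval at N=500, adds one example at N=400, and raises recruitment to 625 to allow for 20% loss to follow-up.

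**The concern.** The study is descriptive, so it has no hypothesis test and the confidence interval is its only statement of uncertainty. Protocol 8.5 chose 500 patients because of the width of that interval. A SAP that names an interval for a secondary clinical outcome, but not for the two primary proportions, seems to leave out the quantity the study was sized on. A programmer who followed 10.1 to the letter could produce tables of counts and percentages alone, and the results would then depart from the protocol.

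A second worry concerns the precision shown in 8.5. The 625 covers loss to follow-up only. The same section says that low viral load will cut the number contributing further, but gives no rate. If far fewer than 500 patients have sequences that can be compared, the tabulated intervals will be too narrow a guide.

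**Working it through.** **Step 1: the texts side by side.**

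| Result | Protocol | SAP |
|---|---|---|
| Epitope change (primary 1) | 95% CI, by the general rule in 8.7.1 | 10.1: counts and percentages; CI not named |
| Spike change (primary 2) | 95% CI, by the general rule in 8.7.1 | 10.1: counts and percentages; CI not named |
| VOC/VUI proportion | 95% CI, by the general rule in 8.7.1 | 10.2: counts and percentages; CI not named |
| Undetectable virus | 95% CI, explicit in 8.7.1.2 | 10.2: summary by visit; CI not named |
| Clinical outcomes | 95% CI, explicit in 8.7.1.2 | 10.2: 95% CI named |

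Nothing in the SAP cancels the protocol's rule, and 8.1 expects intervals on some proportions. The SAP is therefore silent; it does not contradict the protocol. Because the shells are not available, no output is shown to lack an interval.

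**Step 2: can the interval be formed from what the SAP does specify?** It needs a count, a denominator and a method.

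- Count: specified in 10.1.
- Denominator: "Unless stated otherwise, the calculation of percentages will be based on the total number of patients with non-missing data" (SAP 8.1). Section 12.2.5.2 says the same and leaves special cases to footnotes or programming notes. SAP 8.2 limits treatment-emergent results to subjects with both baseline and post-baseline records.
- Method: not in the SAP, but Protocol 8.5 names one for these endpoints.

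**Step 3: reproduce the figures in Protocol 8.5.** With q = 1 − p and z = 1.960 (z² = 3.841), the continuity-corrected score limits are

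L = [2np + z² − 1 − z√(z² − 2 − 1/n + 4p(nq + 1))] / [2(n + z²)]

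U = [2np + z² + 1 + z√(z² + 2 − 1/n + 4p(nq − 1))] / [2(n + z²)]

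- n = 500, p = 0.50: L = [502.841 − 1.960 × √503.839] / 1007.683 = 0.455. By symmetry U = 0.545. The protocol gives 45.5% to 54.5%.
- n = 500, p = 0.09: L = [92.841 − 1.960 × √165.999] / 1007.683 = 0.067. U = [94.841 + 1.960 × √169.279] / 1007.683 = 0.119. The protocol gives 6.7% to 11.9%.
- n = 400, p = 0.50: L = [402.841 − 1.960 × √403.839] / 807.683 = 0.450, so U = 0.550. The protocol gives 45.0% to 55.0%.
- Recruitment: 500 / (1 − 0.20) = 625, as stated.

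All eight rows of Table 2 agree to three decimals.

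**Step 4: how much does N=400 matter at the rates quoted in 8.5?**

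| Rate | N=500 | Width (points) | N=400 | Width (points) |
|---|---|---|---|---|
| Epitope 9% | 6.7–11.9% | 5.2 | 6.5–12.3% | 5.9 |
| Epitope 20% | 16.6–23.8% | 7.2 | 16.3–24.3% | 8.1 |
| Spike 52% | 47.5–56.4% | 8.9 | 47.0–57.0% | 10.0 |
| Spike 80% | 76.2–83.4% | 7.2 | 75.7–83.7% | 8.1 |

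Stopping at 500 enrolled with 20% loss would leave 500 × 0.80 = 400, before any viral-load loss. The protocol's example already covers N=400 at 50%, the rate with the widest interval, so no other rate gives more than 10.0 points there.

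**The case for a change.** The strongest case for a change is that the SAP exists to supply this detail. Protocol 8.7.3 hands the specifics to it, and 10.2 shows that its authors name an interval when they intend one. The word for the covered endpoints in 8.1 is narrower than the protocol's rule. The choice of method can also matter in small samples: with 9% of an assumed 100 patients, the continuity-corrected score interval is 4.5–16.8% and the Wald interval 3.4–14.6%. On precision, the width at 50% would reach 14.2 points with 200 evaluable patients and 20.2 with 100, and results are reported by visit, where numbers may fall.

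Part of this stands. The wording mismatch is real. It is most direct for undetectable virus, where the protocol is explicit, and the same silence covers the VOC/VUI proportion. The SAP also names no interval method.

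The rest carries less weight. The sentences in 10.1 describe rows for individual substitutions, so they are weak evidence that an interval was removed from the overall proportion with any change. The protocol's abstract itself mentions only counts and proportions for undetectable virus and clinical outcomes, which suggests loose drafting and not a decision to omit. The figures for 200 and 100 patients are assumptions, because the documents give no rate of evaluable sequences. Protocol 8.5 says there is no prior information on these exact endpoints, acknowledges the extra loss, and plans to re-assess the target after 200–300 patients. More rows in Table 2 would not alter enrolment or analysis.

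**Conclusion.** No change follows. On intervals, the SAP omits a detail that the protocol supplies: the requirement is in 8.7.1 and 8.7.1.2, and a method for the primary proportions is in 8.5. Naming it again would move no estimate, denominator or conclusion. On precision, 8.5 contains no arithmetic error and already states its main limitation. Going from 500 to 400 patients widens the intervals at the quoted rates by about one point or less (5.2 to 5.9, 7.2 to 8.1, 8.9 to 10.0).

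This rests on two assumptions: that the analysts apply the protocol's standing rule where the SAP is silent, and that the tables show the number evaluated beside each count. The shells could confirm both but are not available. If the tables did appear without intervals, a reader could compute them from the count and denominator, so the consequence would be a reporting omission and not a wrong result.
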